CLINICAL TRIAL PROTOCOL

PLN-74809-IPF-202

Study Title: A randomized, double-blind, dose-ranging, placebo-controlled Phase 2a evaluation of the safety, tolerability and pharmacokinetics of PLN-74809 in participants with idiopathic pulmonary fibrosis (IPF) (INTEGRIS-IPF)

Study Number: PLN-74809-IPF-202

Study Phase: 2a

Product Name: PLN-74809-000

IND Number: 139,998

EUDRACT Number: 2019-002709-23

Indication: Treatment of idiopathic pulmonary fibrosis (IPF)

Sponsor: Pliant Therapeutics Inc.
[name]
[name]

Sponsor Study Director: [REDACTED]

	Date
Original Protocol (v1.0):	11 June 2019
Protocol Amendment 1 (v1.1):	08 April 2020
Protocol Amendment 2 (v2.0):	30 November 2020
Protocol Amendment 3 (v3.0):	19 October 2021

Confidentiality Statement

This document is the property of Pliant Therapeutics. The confidential information in this document may not be used, published or disclosed without the prior written consent of Pliant Therapeutics except to the extent required under applicable laws or regulations.

	
 • Pending favorable review by the DSMB of: 
 ○ All available safety and PK data from this study (Part C) ○ Safety and PK data from study [REDACTED], an ongoing Phase 1 study evaluating the safety, tolerability, and pharmacokinetics of PLN-74809 at multiple doses ranging from 80 to 320 mg in healthy participants, as described in the Investigator’s Brochure 
In Part D, approximately 28 eligible participants will be randomized in a 3:1 ratio (320 mg PLN-74809:placebo) on Day 1 (Visit 2). Randomization will be stratified by use of SoC IPF therapy (pirfenidone or nintedanib) (SoC use; yes or no). Study treatment will be administered for at least 24 weeks. Treatment will continue for all participants in Part D until the last participant enrolled in Part D reaches Week 24. Participants who discontinue study drug for safety reasons prior to completion of 12 weeks (Parts B and C) or at least 24 weeks (Part D) of treatment will be asked to remain in the study to complete all remaining assessments; if this is not feasible, they will be asked to return to the clinic for an Early Termination (ET) visit for follow-up evaluations.
 
The DSMB will assess participant safety at predetermined intervals during the study, including prior to initiating Part D and following the enrollment of the last participant in Part D. [REDACTED]


Study Population:
	
Parts B, C and D of this study intend to enroll approximately 112 participants with mild-to-moderate IPF, who comply with the following eligibility criteria:
 
Inclusion Criteria:
 
 1. Participants, aged 40 years or older 2. Diagnosis of IPF for up to 5 years prior to screening based on American Thoracic Society (ATS)/ European Respiratory Society (ERS)/ Japanese Respiratory Society (JRS)/ Latin American Respiratory Society (ALAT) 2018 guidelines [REDACTED] 
Note: If IPF diagnosis is within > 3 to ≤ 5 years at screening, the participant must have evidence of progression within the last 24 months, [REDACTED]
 
 3. [REDACTED] 4. Diffusing capacity for carbon monoxide (DLco) (hemoglobin-adjusted) ≥ 30%; historical DLco for entry in the study is permitted if within 1 month of screening 5. Participants currently receiving treatment for IPF with nintedanib or pirfenidone are allowed, provided these drugs have been given at a stable dose for at least 3 months before the Screening visit and are expected to remain unchanged during the study (stable dose is defined as the highest dose tolerated by the participant during ≥ 3 months) 6. Estimated glomerular filtration rate ≥ 50 mL/min, according to the Cockcroft-Gault equation 7. Female participants of non-childbearing potential must be surgically sterile or postmenopausal 8. Female participants of childbearing potential must use a contraceptive method with a failure rate of < 1% per year or remain abstinent (refrain from heterosexual intercourse) during the treatment period and for 1 month after the last dose of study treatment. Male participants with female partners of childbearing potential must agree to use contraceptive measures or remain abstinent (refrain from heterosexual intercourse) during the treatment period and for at least 3 months after the last dose of study treatment.

	
9. Participants must agree to abstain from sperm or egg donation for the duration of the study, through to 3 months or 1 month, respectively, after administration of the last dose of study drug.
 
10. Able to read and sign a written informed consent form (ICF)
 
Exclusion Criteria:
 
 1. Receiving any nonapproved agent intended for treatment of fibrosis in IPF 2. [REDACTED] 3. [REDACTED] 4. Any other condition that prevents the correct assessment of spirometry performance (for example a broken rib or chest pain of other origin that prevents adequate forced breathing) 5. Known acute IPF exacerbation or suspicion by the Investigator of such, within 6 months of screening 6. The extent of emphysema is greater than the extent of fibrotic changes on the most recent high-resolution computerized tomography (HRCT) scan (as determined by central reader); a) HRCT scan performed within 2 years of the screening date may be used 7. Severe pulmonary hypertension 8. Smoking of any kind (not limited to tobacco) within 3 months of screening or unwilling to avoid smoking throughout the study 9. Lower respiratory tract infection requiring antibiotics within 4 weeks prior to screening and/or during the screening period 10. History of malignancy within the past 5 years or ongoing malignancy other than basal cell carcinoma, resected noninvasive cutaneous squamous cell carcinoma, or treated cervical carcinoma in situ 11. End-stage liver disease 12. Renal impairment or end-stage kidney disease requiring dialysis 13. History of unstable or deteriorating [REDACTED] or pulmonary disease (other than IPF) within the 6 months prior to screening, including but not limited to the following: 
 a. [REDACTED] b. [REDACTED] c. [REDACTED] d. [REDACTED] 14. Any of the following liver function test criteria above specified limits: total bilirubin $> 1.5 \times$ the upper limit of normal (ULN); aspartate aminotransferase (AST) or alanine aminotransferase (ALT) $> 3 \times$ ULN; alkaline phosphatase $> 2.5 \times$ ULN. 
Note: participants currently receiving nintedanib or pirfenidone as IPF SoC treatment, who have previously presented any liver function test elevations associated with nintedanib or pirfenidone treatment greater than that described above or resulting in dose reduction, treatment interruption, or discontinuation are not eligible.

--	--

	
15. Any of the following at screening: hemoglobin < 10.0 g/dL, or neutrophils < 1500 /mm³, or platelets < 100,000 /mL
 
16. Pregnant or lactating females
 
17. Daily use of phosphodiesterase-5 (PDE-5) inhibitor drugs (e.g., sildenafil, tadalafil, other) (Note: Intermittent use for erectile dysfunction is allowed)
 
18. A medical or surgical condition known to affect drug absorption (e.g., major gastric surgery)
 
19. Surgical procedures planned to occur during the study period
 
20. [REDACTED]
 
21. Has participated in a clinical study with an investigational agent in the 30 days prior to screening or 5 half-lives of the investigational drug, whichever is longer
 
22. Likely to have lung transplantation during the study (being on transplantation list is acceptable)
 
23. Any medical condition that, in the opinion of the Investigator, may make candidates not suitable for the study
 
24. Hypersensitivity to PLN-74809 or to any of the excipients, or placebo
 
25. [REDACTED]

Test Product, Dose, and Mode of Administration:
	
Part B: 40 mg of PLN-74809 or matching placebo administered orally QD Part C: 80 mg or 160 mg of PLN-74809 or matching placebo administered orally QD Part D: 320 mg of PLN-74809 or matching placebo administered orally QD PLN-74809 will be supplied by Pliant as [REDACTED]. Study drug will be taken once daily at approximately 24-hour intervals. Participants will take the study drug [REDACTED] and will drink up to 240 mL (~1 cup of water) [REDACTED].


Duration of Treatment:
	
The duration for Parts B and C of the study will be up to 18 weeks each (up to 4 weeks of screening, 12 weeks of treatment with study drug, and 2 weeks of follow up). The duration for Part D of the study will be variable depending on the study enrollment rate; i.e. the time between enrolling the first and last participant. The minimum duration of participation will be up to 30 weeks for the last participant enrolled (up to 4 weeks of screening, 24 weeks of treatment with study drug, and 2 weeks of follow up) and a maximum of up to 54 weeks for the first participant enrolled (up to 4 weeks of screening, up to 48 weeks of treatment with study drug, and 2 weeks of follow up). The end of study will commence once the last participant reaches 24 weeks of treatment. At that time, all study participants will complete their next scheduled visit (End of Treatment [EoT]) and the 2 weeks of follow up (End of Study [EoS]).

Exploratory Efficacy Assessments:
	
[REDACTED]
 
[REDACTED]
 
[REDACTED]
 
[REDACTED]
 
[REDACTED]
 
[REDACTED]

Pharmacokinetic, Pharmacodynamic, and Pharmacogenomic Assessments
	
 • PK: plasma samples for PK analysis ([REDACTED]) will be obtained • Biomarkers: urine, plasma, and serum samples will be obtained • Pharmacogenomics: a whole blood sample for deoxyribonucleic acid (DNA) isolation will be collected before dosing on Day 1 from each participant in the study

Safety Assessments:
	
Collection of adverse events (AEs), safety laboratory values, vital signs, physical examinations, and [REDACTED]

Statistical Methods:
	
This is a safety study, [REDACTED] [REDACTED] [REDACTED] [REDACTED] [REDACTED] [REDACTED] [REDACTED]
 
In general, data will be summarized using statistical summary methods; graphic presentations of data may also be prepared.

TABLE OF CONTENTS

CLINICAL TRIAL PROTOCOL.....	1
PLN-74809-IPF-202	1
SYNOPSIS.....	2
TABLE OF CONTENTS.....	7
LIST OF IN-TEXT TABLES	10
LIST OF IN-TEXT FIGURES.....	10
LIST OF APPENDICES.....	10
LIST OF ABBREVIATIONS.....	11
1 INTRODUCTION	14
1.1 Summary of Clinical Development	14
1.1.1 Completed Phase 1 Studies (Completed Clinical Conduct)	15
1.1.2 Ongoing Phase 1 Studies	16
1.1.3 Completed Phase 2 Studies (Completed Clinical Conduct)	17
1.1.4 Ongoing Phase 2 Studies	17
1.2 Study Rationale for PLN-74809-IPF-202	18
2 STUDY OBJECTIVES (PARTS B, C, AND D).....	20

ARDS	acute respiratory distress syndrome
AST	aspartate aminotransferase
ATS	American Thoracic Society
AUC ₀₋₂₄	area under the plasma concentration-time curve from time zero to 24 hours
BALF	bronchoalveolar lavage fluid
████	██
C _{max}	maximum observed drug concentration
COVID-19	coronavirus disease 2019
CRO	contract research organization
CTCAE	Common Terminology Criteria for Adverse Events
████	████████████████
████	██
DL _{co}	diffusing capacity for carbon monoxide
DNA	deoxyribonucleic acid
DSMB	Data Safety Monitoring Board
████	████████████████
eCRF	electronic case report form
EDC	electronic data capture
EoS	end of study
ERS	European Respiratory Society

ET	early termination
████	██
FSH	follicle-stimulating hormone
████	████████████████████
GCP	Good Clinical Practice
HIPAA	Health Information Portability and Accountability Act
HRCT	high-resolution computerized tomography
IC ₅₀	50% inhibitory concentration
IC ₈₀	80% inhibitory concentration
IC ₉₀	90% inhibitory concentration
ICF	informed consent form
ICH	International Council on Harmonisation
IEC	independent ethics committee
████	████████████████████
INR	international normalized ratio
IPF	idiopathic pulmonary fibrosis
IRB	institutional review board
IRT	interactive response technology
ITT	intent-to-treat
JRS	Japanese Respiratory Society
MAD	multiple ascending dose
████	██
MedDRA	Medical Dictionary for Regulatory Activities
mRNA	messenger ribonucleic acid
████	██
NOAEL	no observed adverse effect level
████	████████████████████
PCLS	precision cut lung slices
PD	pharmacodynamic(s)

PDE-5	phosphodiesterase -5
PET	positron emission tomography
PK	pharmacokinetic(s)
PRO	patient-reported outcome
PSC	primary sclerosing cholangitis
pSMAD2/3	phosphorylated SMAD2/3
QD	once daily
█	█
█	█
█	█
REB	research ethics board
SAD	single ascending dose
SAE	serious adverse event
SAP	statistical analysis plan
SoC	standard of care
SMAD2/3	family of proteins similar to the gene products of the Drosophila gene 'mothers against decapentaplegic' (Mad) and the C. elegans gene Sma , 2 or 3
SpO ₂	peripheral capillary oxygen saturation
TEAE	treatment-emergent adverse event
TGF-β	transforming growth factor beta
ULN	upper limit of normal
US	United States
█	█

1 INTRODUCTION

Pliant Therapeutics Inc. (Pliant) is developing PLN-74809 for the treatment of idiopathic pulmonary fibrosis (IPF) and primary sclerosing cholangitis (PSC).

IPF is a rare condition, usually of the elderly, characterized by dyspnea and progressive loss of lung function leading to death, with median survival of 3.8 years after diagnosis based on 2014 data in the United States (US). The hallmark honeycomb appearance of IPF on high-resolution computerized tomography (HRCT) is the result of extensive fibrosis [REDACTED]. Although not completely understood, IPF has been proposed to stem from ongoing microinjury to alveolar epithelial cells. Injured epithelium results in upregulation of profibrotic factors such as transforming growth factor beta (TGF- β), which promote fibroblast recruitment, proliferation, and differentiation into fibrogenic myofibroblasts [REDACTED]. As the disease progresses, actively proliferating fibroblasts and myofibroblasts organize into fibroblastic foci and produce excessive fibrillar collagen that results in scarring of the lung which, in turn, leads to distortion of the tissue architecture and loss of function [REDACTED].

As has also been indicated to be the case for other fibrotic conditions, signaling mediated by α_v integrins is central to the control of fibrosis in the lungs. Specific roles proposed for $\alpha_v\beta_6$ in epithelial cells and $\alpha_v\beta_1$ in myofibroblasts for induction of fibrosis are summarized in the Investigator's Brochure for PLN-74809.

PLN-74809 is a small molecule and a selective dual inhibitor of $\alpha_v\beta_6$ and $\alpha_v\beta_1$ integrins (50% inhibitory concentration [IC₅₀] [REDACTED], respectively). Additionally, integrin-ligand binding assays have demonstrated that PLN-74809 is highly selective for $\alpha_v\beta_6$ and $\alpha_v\beta_1$ over other integrin receptors, including those leukocyte-expressed integrins where therapeutic inhibition has previously been associated with significant toxicities (e.g., vedolizumab [$\alpha_4\beta_7$ inhibitor; increased risk of infections, potential risk of progressive multifocal leukoencephalopathy (PML); [REDACTED]] and natalizumab [$\alpha_4\beta_1$ and $\alpha_4\beta_7$ inhibitor; increased risk of PML; [REDACTED]]). PLN-74809 reduced collagen synthesis in mice with bleomycin-induced lung injury, a commonly used experimental model for IPF ([REDACTED]). In ex vivo human IPF lung tissue (precision cut lung slices), treatment with PLN-74809 significantly decreased collagen type 1 α 1 messenger ribonucleic acid (mRNA) expression levels after a 3-day incubation period, providing an indication of antifibrotic activity in IPF. Mice completely deficient for $\alpha_v\beta_6$ function live a normal lifespan ([REDACTED]), suggesting that even full inhibition of such integrins is well tolerated.

1.1 Summary of Clinical Development

PLN-74809 is currently being investigated for the treatment of IPF and PSC.

Seven Phase 1 clinical studies in healthy participants have completed clinical conduct (Including Part 1 of Study [REDACTED]), with safety data, pharmacokinetic (PK) data, and preliminary pharmacodynamic (PD) data available. [REDACTED]

[Redacted text block]

1.1.1 Completed Phase 1 Studies (Completed Clinical Conduct)

[Redacted text block]

[Redacted text block]

[Redacted text block]

[Redacted text block]

[Redacted text block]

[Redacted text block]

[Redacted text block]

[Redacted text block]

[Redacted text block]

[Redacted text block]

[Redacted text block]

[Redacted text block]

[Redacted text block]

1.1.2 Ongoing Phase 1 Studies

[Redacted text block]

[Redacted text block]

[Redacted text block]

[Redacted text block]

[Redacted text block]

[REDACTED]

1.1.3 Completed Phase 2 Studies (Completed Clinical Conduct)

[REDACTED]

1.1.4 Ongoing Phase 2 Studies

[REDACTED]

1.2 Study Rationale for PLN-74809-IPF-202

PLN-74809 is a selective, small molecule antagonist of integrins $\alpha_v\beta_6$ and $\alpha_v\beta_1$, with antifibrotic activity. PLN-74809 prevents $\alpha_v\beta_6$ and $\alpha_v\beta_1$ from binding to the arginine-glycine-aspartate sequence of the latency associated peptide of the TGF- β precursor protein, thereby blocking the release of the activated form of TGF- β 1 and preventing binding to its receptors and activation of pathways relevant to fibrogenesis. PLN-74809 was demonstrated to be a potent and selective inhibitor of $\alpha_v\beta_6$ and $\alpha_v\beta_1$ integrins (human and murine) exhibiting geometric mean 50% inhibitory concentration (IC₅₀) values of [REDACTED] and [REDACTED] against the human receptors, respectively.

Precision cut lung slices (PCLS) generated from IPF patient lungs collected during transplant were used to evaluate the ability of PLN-74809 to block TGF- β activation and collagen gene expression in fibrotic human lung tissue ex vivo. Following 7 days incubation with PLN-74809 ([REDACTED]), collagen gene expression and SMAD2 phosphorylation (a marker of TGF- β signaling) in IPF patient PCLS were significantly reduced by approximately [REDACTED]. Further studies with bleomycin-injured mouse PCLS also showed significant reductions in collagen gene expression observed at concentrations of PLN-74809 as low as [REDACTED].

In vivo efficacy studies of PLN-74809 were performed using the bleomycin mouse model of pulmonary fibrosis. In a prophylactic treatment study (PLN-74809 administered orally or via minipump from [REDACTED] post-bleomycin challenge), PLN-74809 significantly decreased Ashcroft score, total hydroxyproline levels in lung tissue, and phosphorylation of [REDACTED] in lung tissue, confirming inhibition of collagen deposition and TGF- β signaling. Similar effects were observed with therapeutic treatment with PLN-74809 in the bleomycin model (oral administration from [REDACTED] days post-bleomycin challenge). Lung hydroxyproline levels were significantly reduced and morphometric analysis of lung tissue showed a dose-dependent and significant reduction in interstitial fibrillar collagen deposition in mice treated with PLN-74809.

The main purpose of the current study is to confirm that PLN-74809 is well tolerated by participants with IPF, whether as monotherapy or as an add-on to standard of care (SoC), and that the drug concentrations are similar to those previously found in healthy participants. [REDACTED]

[REDACTED]

Part D of the study will evaluate approximately 28 participants at the 320 mg dose for at least 24 weeks to further characterize the safety profile of PLN-74809. In Part D, ongoing safety and [REDACTED] assessments will continue until the last participant reaches 24 weeks of the study; therefore, safety and [REDACTED] assessments may extend to 48 weeks in participants randomized earlier in the study. [REDACTED]

[REDACTED]

The extended duration of exposure at the highest dose planned to be evaluated in Part D

(320 mg QD) is consistent with the intended use of PLN-74809 to treat the chronic and progressive fibrosis that characterizes IPF.

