* Treatment will continue for all participants in Part D until the last participant enrolled in Part D reaches Week 24. All participants will complete visits every 8 weeks after the Week 24 visit until such time as the last participant enrolled has completed the Week 24 visit. At this time, all participants will be contacted to return and complete the Final On-Treatment Visit. All participants will have a Week 26 visit, which will be considered the End of Treatment Visit for the last participant to complete the Week 24 Visit.

Potential participants who provide written informed consent will be screened for study eligibility up to 28 days before administration of the first dose of study drug.

In Parts B, C and D, eligible participants will be randomized on Day 1 (Visit 2). Randomization will be stratified by use of SoC IPF therapy with pirfenidone or nintedanib (SoC use; yes or no).

In Part B, 29 eligible participants were randomized in a 3:1 ratio (active:placebo) and treated for 12 weeks.

In Part C, approximately 56 eligible participants will be randomized in a 3:3:2 ratio (80 mg PLN-74809:160 mg PLN-74809:placebo) and treated for 12 weeks in parallel treatment groups.

In Part D, an additional PLN-74809 dose of 320 mg is planned for evaluation based on the following criteria:

- Part C has been completely enrolled (ie, 56 participants have been randomized)
- Pending favorable review by the DSMB of:
 - All available safety and PK data from this study (Part C)
 - Safety and PK data from study [REDACTED], as described in the Investigator’s Brochure

In Part D, approximately 28 eligible participants will be randomized in a 3:1 ratio (320 mg PLN-74809:placebo) on Day 1 (Visit 2). Randomization will be stratified by use of SoC IPF therapy (pirfenidone or nintedanib) (SoC use; yes or no). Study treatment will be administered for at least 24 weeks. Treatment will continue for all participants in Part D until the last participant enrolled in Part D reaches Week 24.

In Parts B and C, study drug will be administered at the investigational site on Day 1 and at Weeks 4 and 12. In Part D, study drug will be administered at the investigational site on Day 1 and at Weeks 4, 12, and 24. Participants will self-administer the study drug on an outpatient basis on all other days. In Parts B and C, participants will return to the study site for on-treatment evaluations on Day 1 and at Weeks 2, 4, 8, and 12 (see Schedule of Events in [Appendix 1](#)).

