8.7 Clinical Laboratory Adverse Events

Abnormal laboratory findings (eg, clinical chemistry, hematology and urinalysis) or other abnormal assessments (eg, ██████, vital signs) per se are not reported as AEs. However, those abnormal findings that are deemed clinically significant or are associated with signs and/or symptoms must be recorded as AEs if they meet the definition of an AE, as described in [Section 8.2](#) (or recorded as an SAE if they meet the criteria of being serious, as described in [Section 8.8](#)). Clinically significant abnormal laboratory or other abnormal findings that are detected after consent or that are present at baseline and worsen after consent are included as AEs (and SAEs if serious).

The Investigator should exercise his/her medical and scientific judgment in deciding whether an abnormal laboratory finding or other abnormal assessment is clinically significant. Usually, the abnormality should be associated with a clinically evident sign or symptom, or be likely to result in an evident sign or symptom in the near term, to be considered clinically significant. A clinically significant laboratory abnormality in the absence of clinical symptoms may jeopardize the participant and may require intervention to prevent immediate consequences. For example, a markedly low serum glucose concentration may not be accompanied by coma or convulsions, yet be of a magnitude to require glucose administration to prevent such sequelae.

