12 PLANNED STATISTICAL METHODS

12.1 General Considerations

This is a safety study with exploratory efficacy and biomarker assessments; as such, no statistical hypotheses are being tested. In general, data will be summarized using statistical summary methods; graphic presentations of data may also be prepared. The contract research organization (CRO) will be responsible for the preparation of tables and listings and will assist in the preparation of figures, which may be done by Sponsor personnel. A statistical analysis plan (SAP), prepared and agreed before final database lock, will describe the analytic approach and methods in more detail.

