6.3.6 Data Displays

All clinical data tabulations, figures and listings will be generated as individual Rich Text Format (.rtf) files using [REDACTED]¹. Data summaries and graphical analyses will be reported within Section 14 of the CSR and individual participant data listings within Appendix 16.2 of the CSR.

Participant disposition, baseline characteristics, demographic, compliance, concomitant medication, and adverse event data will be presented by treatment group and overall. Other safety data will be presented by treatment group only.

Please note: Data from study Part A will be listed only.

Treatment group labels will be displayed as follows:

PLN-74809	PLN-74809	PLN-74809	PLN-74809	All	
(40 mg)	(80 mg)	(160 mg)	(320 mg)	PLN-74809	Placebo
(N=XX)	(N=XX)	(N=XX)	(N=XX)	(N=XX)	(N=XX)

QMD [REDACTED]	[REDACTED]
Confidentiality Statement	
This document is the property of [REDACTED] and may not be duplicated, copied, altered or removed from company without prior approval from [REDACTED] or in compliance with [REDACTED].	

[REDACTED]

Controlled Quality Management Document		
	Sponsor:	Pliant Therapeutics Inc.
	Protocol Number:	PLN-74809-IPF-202
STATISTICAL ANALYSIS PLAN. PHASE 2-3-4		

Listings will be sorted in the following order, study part (Parts B/C/D/A), treatment group, participant number, parameter, and visit unless otherwise stated. All data will be listed, participants who were not randomized will be displayed after the randomized treatment groups.

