6.15.1 Adverse Events

AE analyses will be presented by the treatment received for the Safety Population. Tabulations will be presented overall and by SoC (Yes, No).

AEs will be collected from the time of informed consent through completion of the participant's last study visit.

A treatment emergent adverse event (TEAE) is defined as:

- Any AE that has an onset on or after the first dose of study drug through completion of the last study visit.
- Any pre-existing AE that has worsened in severity on or after the first dose of study drug through completion of the last study visit.

AEs occurring prior to first dose are considered non-treatment emergent and will be listed only.

The Investigator will determine the relationship of the AE to treatment (Related, Not Related). If an AE has missing relationship it is assumed to be related to the study drug for analysis purposes.

Severity of the AE will be graded using the Common Terminology Criteria for Adverse Events (CTCAE) grading system (Version 5.0): Grade 1 (Mild), Grade 2 (Moderate), Grade 3 (Severe), Grade 4 (Life-Threatening), Grade 5 (Fatal). Grade 3 (Severe) will be assumed for an AE with missing grade.

An overall summary of AEs (incidence and number of events) will be presented by treatment group and overall, for the following:

- Any AE
- TEAE
- TEAE Related to Study Drug

QMD [REDACTED]	[REDACTED]
Confidentiality Statement	
This document is the property of [REDACTED] and may not be duplicated, copied, altered or removed from company without prior approval from [REDACTED] or in compliance with [REDACTED].	

[REDACTED]

Controlled Quality Management Document		
	Sponsor:	Pliant Therapeutics Inc.
	Protocol Number:	PLN-74809-IPF-202
STATISTICAL ANALYSIS PLAN. PHASE 2-3-4		

- TEAE Related to a Study Procedure
- Serious TEAE
- Serious TEAE Related to Study Drug
- TEAE of CTCAE Grade 3 or Higher
- TEAE of CTCAE Grade 3 or Higher Related to Study Drug
- TEAE Leading to Interruption of Study Drug
- TEAE Leading to Withdrawal of Study Drug
- TEAE Leading to Early Termination from Study
- TEAE Leading to Death

Summaries of TEAEs (incidence and number of events) will be presented by SOC and PT, by treatment group and overall, for the following:

- TEAE
- TEAE Related to Study Drug
- Serious TEAE
- Serious TEAE Related to Study Drug
- TEAE Related to a Study Procedure
- TEAE of CTCAE Grade 3 or Higher
- TEAE of CTCAE Grade 3 or Higher Related to Study Drug
- TEAE Leading to Interruption of Study Drug

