6.15.2 Laboratory Data

Descriptive statistics of the observed values and change from baseline will be presented by treatment group and visit for each continuous hematology, serum chemistry, coagulation, and urinalysis parameter. Shift tables for the change from baseline in categorical parameters will be presented in the natural order of the outcome where possible.

Summaries and listings will be presented using the Système International (SI) unit for each parameter as received from the analytical laboratory.

Each measurement (for continuous data and for categorical data where provided) will be classed as below, within, or above normal range, based on ranges supplied by the laboratory used. Shift tables in relation to the normal range from baseline to each follow-up visit will be presented.

In addition, any confirmed liver abnormalities, identified per Section 6.2.19, will be summarized by treatment group and listed.

All individual laboratory data (including pregnancy testing data) will be listed. Any liver abnormalities identified will be provided as a separate listing.

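### Laboratory, liver and vital-sign summaries are not split by standard-of-care (SoC) use, although tolerability with and without SoC is the stated main purpose

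*Protocol*

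**What the plan says.** Protocol 1.2 (Study Rationale) gives the main purpose as confirming that "PLN-74809 is well tolerated by participants with IPF, whether as monotherapy or as an add-on to standard of care (SoC"). Protocol 3.1 builds the factor into the design: "Randomization will be stratified by use of SoC IPF therapy with pirfenidone or nintedanib (SoC use; yes or no").

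The SAP carries it into the AE analysis. SAP 6.15.1 states: "Tabulations will be presented overall and by SoC (Yes, No"). It does not visibly do so elsewhere in safety:

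- SAP 6.15.2 gives laboratory statistics by treatment group and visit, with normal-range shift tables and no mention of SoC. On the liver, "any confirmed liver abnormalities, identified per Section 6.2.19, will be summarized by treatment group and listed".
- SAP 6.15.3 gives vital signs by treatment group at each visit.
- SAP 6.3.6 lists the data shown by treatment group plus an overall column, then adds: "Other safety data will be presented by treatment group only".
- SAP section 9, item 1, names AE summaries and efficacy for an added presentation. The end of that item is redacted.

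Protocol 8.7 says that abnormal laboratory and other findings "per se are not reported as AEs", but requires clinically significant or symptomatic ones to be recorded as AEs when they meet the AE definition. Protocol 12.1 states that "no statistical hypotheses are being tested".

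**The concern.** The purpose has two arms, use alone and use on top of SoC, and the trial randomizes within that factor. AEs can be read in each arm of the question, but the summaries of objective safety data cannot. A dose column that mixes SoC users and non-users shows a weighted average of two strata.

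The AE split does not fully cover this. A change that the investigator does not judge clinically significant, and that causes no symptoms, stays out of the AE tables. The same holds for a liver abnormality that meets the SAP criteria but is not recorded as an AE. The laboratory and vital-sign summaries are where such changes would appear. SAP section 9, item 6, also removed the summaries of laboratory parameters by CTCAE grade, so there are fewer of them.

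At stake is whether those summaries can support a statement about tolerability in each setting. Protocol 6.6.1 notes that this is the first study in which repeated doses of PLN-74809 and nintedanib may be given together.

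**Working it through.** **1. The plan's own totals.** Inputs are from Protocol 6.4.

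- Part B: 28 at 3:1 gives 28 × 3/4 = 21 active and 7 placebo.
- Part C: 56 at 3:3:2 gives 56 × 3/8 = 21 on 80 mg, 21 on 160 mg, and 56 × 2/8 = 14 placebo.
- Part D: 28 at 3:1 gives 21 active and 7 placebo.
- Active 21 × 4 = 84; placebo 7 + 14 + 7 = 28; total 112.

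This reproduces the 112, 84 and 28 in Protocol 3.1 and the 21 per dose in Protocol 12.2. Protocol 3.1 also gives 29 randomized in Part B, which would make 113 and changes nothing here. Every part is 3:1 active to placebo (21:7, 42:14, 21:7), so pooling across parts keeps the two pooled columns balanced by part.

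**2. Stratum sizes.** The SoC share s is not given, so it is assumed to lie between 0.5 and 0.9. Expected numbers with SoC are n × s, and without SoC n × (1 − s).

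| s | Per dose (21): SoC / no SoC | All active (84): SoC / no SoC | Placebo (28): SoC / no SoC |
|---|---|---|---|
| 0.5 | 10.5 / 10.5 | 42 / 42 | 14 / 14 |
| 0.7 | 14.7 / 6.3 | 58.8 / 25.2 | 19.6 / 8.4 |
| 0.9 | 18.9 / 2.1 | 75.6 / 8.4 | 25.2 / 2.8 |

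**3. Dilution.** The pooled value is s × (value with SoC) + (1 − s) × (value without SoC). Stratified randomization makes s similar in active and placebo, so the same formula applies to their difference.

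| s | Share kept if shift is in SoC users only | Share kept if shift is in non-users only |
|---|---|---|
| 0.5 | 50% | 50% |
| 0.7 | 70% | 30% |
| 0.9 | 90% | 10% |

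Illustration with assumed abnormality rates of 20% in the affected stratum and 2% in the other:

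- Affected stratum is non-users: 0.5 × 2% + 0.5 × 20% = 11.0%; 0.7 × 2% + 0.3 × 20% = 7.4%; 0.9 × 2% + 0.1 × 20% = 3.8%.
- Affected stratum is SoC users: 11.0%; 0.7 × 20% + 0.3 × 2% = 14.6%; 0.9 × 20% + 0.1 × 2% = 18.2%.

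**4. What a split could show.** With zero events in n participants, the exact two-sided 95% upper limit is 1 − 0.025^(1/n).

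- One whole dose group, n = 21: 16%.
- Non-users in one dose group, n = 10, 6 or 2: 31%, 46% or 84%.
- Non-users in All PLN-74809, n = 42, 25 or 8: 8%, 14% or 37%.

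The split is therefore more useful for pooled active versus pooled placebo than by dose.

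**The case against.** The strongest reply is that the primary endpoint is AEs, and AEs are tabulated by SoC. Protocol 8.7 requires clinically significant findings to be recorded as AEs, and Protocol 8.8.2 treats any clinically relevant laboratory deterioration as one. Confirmed liver abnormalities are counted and listed, and all laboratory data and medications are listed, so individual cases can be traced to SoC use. Protocol 12.5.1 itself asks for laboratory summaries by treatment and dose, not by SoC. All of this stands and confines the gap to sub-clinical changes and liver abnormalities not recorded as AEs. It does not close the gap: a listing does not compare active with placebo within a stratum.

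A reader might go further on three points that the documents do not support.

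- *SAP 6.3.6 forbids an SoC split.* In context, its restriction contrasts with the overall column. The same paragraph mentions no SoC split for AEs either, yet 6.15.1 provides one.
- *The eligibility note shows that liver tests are where the strata will differ.* The note to exclusion criterion 14 mentions "liver function test elevations associated with nintedanib or pirfenidone treatment", but it excludes current SoC users whose past elevations exceeded the limits or led to a change in that treatment. It removes known reactors and does not show where or in which direction the strata differ.
- *One stratum is credited with the other's abnormalities.* Stratified randomization balances background SoC effects between active and placebo. The result is dilution, not misattribution.

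Small numbers are a fair objection to over-reading the split. With 5 events among 84 active participants, 63 of them on SoC (75%, assumed), all 5 would fall in the SoC stratum by chance with probability (63 × 62 × 61 × 60 × 59) / (84 × 83 × 82 × 81 × 80) = 23%. A yes/no split also merges nintedanib with pirfenidone.

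**Conclusion.** The point holds in a limited form. In the readable text, the summaries of laboratory data, confirmed liver abnormalities and vital signs lack the split that the stated purpose calls for and that the AE tables already have. Sub-AE signals confined to one stratum are diluted in those summaries. The dilution is severe only when the signal lies in the smaller stratum: at an assumed 90% SoC share, non-users' signals keep 10% of their size and SoC users' signals keep 90%.

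It would be too strong to say that a stratum-specific signal is averaged away, or that the objective safety data cannot address the purpose. The AE tables, liver counts and listings all carry part of the answer.

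The conclusion rests on an SoC share that the documents do not give and on text that is partly redacted. The table list in SAP section 11, section 6.2.19 and the end of section 9, item 1, cannot be read, so an SoC-split table may exist there.

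**What to change.** In SAP 6.15.2 and 6.15.3, state that the confirmed liver-abnormality summary, the normal-range shift tables and the vital-sign changes are repeated by SoC (Yes, No), using the randomization stratum, for All PLN-74809 versus pooled placebo. Show any dose-by-SoC cells as counts only. Keep the sentence in SAP 6.3.6, because it governs the overall column, and add an exception for displays specified in 6.15.2 and 6.15.3. If the redacted table list already contains these tables, only the wording needs aligning.

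The cost is a few lines of SAP text and a by-variable in existing table programs. No error rate is affected, since no hypotheses are tested, and SAP section 6 already allows additional tables with documented justification. The downside is small non-SoC cells: about 8 to 42 of 84 active and 3 to 14 of 28 placebo as the SoC share runs from 90% to 50%. The displays should be labelled descriptive, and an empty cell should not be read as evidence of no effect.
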